Potential Risks

This study poses no more than minimal risks to participants. Caregivers may experience emotional discomfort when completing psychological instruments (coping with cancer self-efficacy, distress, burden, quality of life), but this is not expected to be greater than that encountered during routine psychological examination. Caregivers may potentially experience discomfort when completing workbook activities; however, the ultimate goal of these activities is to reduce negative psychological effects associated with providing care. The primary risk to all participants is loss of privacy and we will take appropriate steps (see confidentiality and privacy) to prevent this.

Likelihood of Risks. Risks associated with this study are unlikely.

Minimizing Risks. All study staff will be trained to interview in a sensitive manner. We will explain to participants that they do not have to complete any assessments that they do not wish to complete and that they may withdraw from participation at any time. Furthermore, caregivers' participation in the intervention is preference based, so they can opt out of modules. Caregiver psychological distress (anxiety and depression) data will be reviewed immediately and if levels are high, we will provide caregivers with contact information for the psychosocial oncology professionals at the cancer center. [name] has training in clinical psychology and will assist with this process when necessary. All investigators will maintain current institutional protection of human subjects credentials.

Confidentiality and Privacy

Confidentiality will be protected by collecting only information needed to assess study outcomes, minimizing to the fullest extent possible the collection of any information that could directly identify subjects, and maintaining all study information in a secure manner. To help ensure subject privacy and confidentiality, only a unique study identifier will appear on the data collection form. Any collected patient/caregiver identifying information corresponding to the unique study identifier will be maintained on a linkage file, stored separately from the data. The linkage file will be kept secure, with access limited to designated study personnel. Following data collection subject identifying information will be destroyed three years after closure of the study, consistent with data validation and study design, producing an anonymous analytical data set. Data access will be limited to study staff. Data and records will be kept locked and secured, with any computer data password protected. No reference to any individual participant will appear in reports, presentations, or publications that may arise from the study. Caregivers will be offered a private room away from the patient to complete surveys and will also have the option to complete surveys by phone with a study researcher. All interviews and sessions with the study interventionist will be completed away from the patient in a private room or by phone, if necessary. Use of study i-Pads does not need to occur in a private room; caregivers may choose to use the devices when patients are receiving treatment.

Potential Benefits of the Proposed Research. Caregivers may experience improvements in self-efficacy (in coping with cancer and abbreviated progressive muscle relaxation) psychological distress, burden, and QOL when participating in the intervention.

Why Risks are Reasonable in Relation to Benefits. The proposed intervention is highly unlikely to pose risks to participants. The minimal risk is outweighed by the potential benefits of the intervention for the caregiver.

Data and Safety Monitoring

The principal investigator will be responsible for the overall monitoring of the data and safety of study participants. The principal investigator will be assisted by other members of the study staff.

Reporting of Unanticipated Problems, Adverse Events or Deviations

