Approximately 3.5 million people provide care for patients with cancer [16]. Although caregiving can be personally rewarding [17], studies have overwhelmingly demonstrated a negative impact on cancer caregivers, including poor quality of life, risk of clinical depression, sleep disturbance, fatigue, pain, loss of physical strength, loss of appetite, and weight loss [18-20]. Studies focused on HNC caregivers are sparse. The limited literature describes a high prevalence of agoraphobia (anxiety disorder) [21], depression [22], and a high fear of patient cancer recurrence [23], with caregivers reporting poorer psychological health compared to patients and the general population [24]. Our research has shown that

during patient RT treatment, HNC caregivers experience increased schedule burden, decreased esteem, poorer self-reported health, and an abnormal cortisol response (dysregulated cortisol slope) from treatment initiation to five weeks into patient's radiotherapy (RT) [25]. HNC caregivers have unmet informational needs and desire psychological support, self-help groups, and help with coping strategies [26-28]. In one study, most spouses of laryngectomized cancer patients desired to learn relaxation methods [29]. Such services can be addressed in a psycho-educational (education pertaining to emotional well-being) and stress management intervention. Our own work has highlighted high interest in wellness programs in HNC caregivers [30].

Psychosocial interventions for informal caregivers have successfully improved burden, depression, subjective well-being, perceived caregiver satisfaction, and ability/knowledge, with multiple component interventions more effectively reducing burden versus single component interventions [31]. However, HNC caregivers have been neglected. One study[32] did evaluate the feasibility of a one-day 6-hour workshop to facilitate coping among HNC patients and family members, but the workshop was not restricted to those providing care. Although participants were highly satisfied with the intervention, only 19% of families approached agreed to participate. Barriers to recruitment and participation included a lack of interest in seeking family support or logistical barriers. Our proposed study will overcome these barriers by providing caregivers with an easily accessible intervention that offers several choices designed to meet their specific preferences.

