Aim 2a: To obtain preliminary data on caregiver intermediate (self-efficacy for (a) coping with cancer and (b) abbreviated progressive muscle relaxation) and outcome variables (burden, psychological distress, quality of life) in intervention caregivers and waitlist control caregivers at the start of radiation (T1), end of radiation (T2), and 6-weeks post-radiation (T3).

Aim 2b: To compare intermediate (self-efficacy for (a) coping with cancer and (b) abbreviated progressive muscle relaxation) and outcome variables (burden, psychological distress, quality of life) between intervention caregivers and waitlist control caregivers at T1, T2, and T3.

Hypothesis: (Aim 2a) *Intermediate and outcome variables will improve in intervention caregivers post-intervention compared to pre-intervention and (Aim 2b) intervention caregivers will have better intermediate (higher self-efficacy for a) coping with cancer, and b) abbreviated progressive muscle relaxation) and outcome variables (less burden, less psychological distress, higher QOL) at T2 compared to waitlist control caregivers.*

Aim 3: To obtain preliminary data on caregiver cortisol response (cortisol slope, cortisol awakening response, area under the curve, and intra-individual cortisol variability) at T1 – T3 in intervention caregivers and waitlist control caregivers.

Hypothesis: *Intervention caregivers will demonstrate a more normal (steeper) diurnal cortisol rhythm (slope) at T2 compared to waitlist control caregivers.*

Aim 4: To refine intervention procedures and materials for future studies by examining: a) qualitative data from caregivers and interventionist notes and b) quantitative data regarding module utilization.

Methods and Measures

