We will use a mixed effects model with a random subject effect and time (T1,T2,T3), group, and a group by time interaction to model change in the intermediate variables (self-efficacy for (a) coping with cancer (CI) and (b) PMR) and outcome variables (burden (CRA), depression (CESD), anxiety (PROMIS Short Form-Anxiety 7a), and QOL (CQoL-Canc), by group from T1 to T2 to T3). We will use linear contrasts to compare the intervention to the control group at T1, T2, and T3. In exploratory analyses we will model the relationship between each outcome and the intermediate variable, by including the intermediate variable as a fixed effect in the model. These results are exploratory due to concurrent measurement with outcome variables; in future studies we would capture potential mediators at an intermediate time point.

Aim 3: To obtain preliminary data on caregiver cortisol response (cortisol slope, cortisol awakening response, area under the curve, and intra-individual cortisol variability) at T1 – T3 in intervention caregivers and waitlist control caregivers.

Analysis Plan: Analyses for Aim 3 will be conducted using data from caregivers who were not excluded from the saliva portion of the study. Several summary measures will be derived from the three daily cortisol values, including the mean levels at each time, the mean cortisol awakening response (CAR – change in cortisol from awakening to 30 minutes), the area under the curve (AUC), the diurnal slope (change in cortisol between awakening and bedtime), and the intraindividual cortisol variability, which will be estimated using the methods as described in Sannes et al.[53] to assess group differences in cortisol parameters. We will use a mixed model to evaluate differences between the groups in these parameters at times T1 and T2 and T3. For a subset of the sample who completed measures on intermediate and outcome variables and cortisol, in exploratory models, we will include the cortisol summary measures as predictor variables in the models described for Aim 2 above.

Aim 4: To refine intervention procedures and materials for future studies by examining: a) qualitative data from caregivers and interventionist notes and b) quantitative data regarding module utilization.

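### The Aim 2a hypothesis is an uncontrolled within-arm improvement; where caregivers decline during RT, it would miss a benefit that only offsets the decline, and no baseline-referenced between-arm contrast is named

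*Combined protocol and SAP*

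**What the plan says.** The Objectives give Aim 2 one hypothesis in two parts. The Aim 2a part is "Intermediate and outcome variables will improve in intervention caregivers post-intervention compared to pre-intervention". The Aim 2b part says that intervention caregivers will do better on the same variables "at T2 compared to waitlist control caregivers". The stated objective of Aim 2a is broader than its hypothesis: it is to gather preliminary data in both arms at T1, T2 and T3.

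The Background, Rationale and Context section reports from the team's own research that "during patient RT treatment, HNC caregivers experience increased schedule burden, decreased esteem, poorer self-reported health", together with a dysregulated cortisol slope, "from treatment initiation to five weeks into" the patient's RT. It gives the direction of change, with no magnitude or SD.

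The Analytical Plan for Aims 2a and 2b states: "We will use a mixed effects model with a random subject effect and time (T1,T2,T3), group, and a group by time interaction". The only contrasts it names are these: "We will use linear contrasts to compare the intervention to the control group at T1, T2, and T3". It names no within-arm contrast from T1 and no between-arm contrast of change from T1.

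**The concern.** Aim 2a asks whether caregivers who receive the intervention get better over time. Over the RT period the protocol itself gives reason to expect some measures to get worse. Schedule, esteem and health are three of the five Caregiver Reaction Assessment (CRA) domains listed in Table 2, and the CRA is the trial's burden outcome. RT is planned for 6-7 weeks, so the reported five weeks cover 5/7 = 71% to 5/6 = 83% of the T1 to T2 interval.

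An intervention that held burden steady while control caregivers declined would be doing its job, yet the Aim 2a hypothesis would not be supported. Aim 2b could then point the other way on the same data, and the protocol does not say which reading counts. The Analytical Plan also intends the trial to supply effect-size estimates for a larger study. If a within-arm change were carried forward as that effect size, it would be wrong by the whole of the natural drift.

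**Working it through.** **What the plan quantifies.** The sample size rests on feasibility, and no effect size, SD or power is stated for Aim 2, so there is no figure of the plan's to reproduce on this point. The precision figures that are given are for other quantities and are sound: 40/56 = 71.4%, and 1.96 × sqrt(0.714 × 0.286 / 56) = 11.8 points; for 80% retention of 40, 1.96 × sqrt(0.8 × 0.2 / 40) = 12.4 points. Both agree with the stated ±12%.

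**Algebra.** Let d be the natural drift from T1 to the later visit and e the intervention effect, with positive values meaning better.

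- Expected change in the intervention arm = d + e.
- Expected change in the control arm = d.
- Difference between arms in change = (d + e) − d = e.
- Difference between arms at T2 = e as well, because randomisation makes the expected T1 difference zero.

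If d = −e, the within-arm change has expectation zero while both between-arm quantities still equal e.

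**Illustration.** From the documents: 20 caregivers per arm, or 16 at the 80% retention used as an example under Sample Size (0.8 × 20). Assumed, because the documents give no values: SD of 1 at each visit, correlation r between visits of 0.3 to 0.7, and the values of d and e below. SD of change = sqrt(2(1 − r)), which is 1.18, 1.00 and 0.77 at r = 0.3, 0.5 and 0.7. Tests are two-sided at 5%, with power from the noncentral t. The within-arm test has noncentrality (d + e) × sqrt(n) / SD of change. The between-arm test of change has noncentrality e / (SD of change × sqrt(2/n)). The table gives the probability of a significant result in the favourable direction, n = 20 per arm, at r = 0.5 with the range over r = 0.3 to 0.7.

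| Drift d | Effect e | Within-arm | Between-arm change |
|---|---|---|---|
| −0.5 | 0.5 | 0.025 (at every r) | 0.34 (0.26 to 0.51) |
| −0.3 | 0.5 | 0.13 (0.11 to 0.19) | 0.34 (0.26 to 0.51) |
| −0.3 or −0.5 | 0 | about 0.001 or less | 0.025 |
| +0.3 | 0 | 0.25 (0.19 to 0.38) | 0.025 |

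At 16 per arm and r = 0.5, the between-arm figure in the first row falls from 0.34 to 0.28.

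**Which between-arm contrast.** With SD 1 at each visit, the variances are:

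- T2 level contrast: 2/n.
- Plain change contrast: 4(1 − r)/n, a ratio to the level contrast of 2(1 − r) = 1.4, 1.0 and 0.6 at r = 0.3, 0.5 and 0.7.
- T2 contrast adjusted for T1: about 2(1 − r²)/n, a ratio of 1 − r² = 0.91, 0.75 and 0.51.

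The plain change contrast loses precision against the T2 level contrast when r is below 0.5. The adjusted contrast has the smallest variance at all three correlations.

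**The case against.** The strongest reply is that the controlled analysis already exists. The second half of the same hypothesis compares the same variables with the randomised control at T2. Randomisation follows the baseline assessment, so that contrast estimates the intervention effect without bias. The group by time term in the model is itself the between-arm difference in change, and lacks only a named contrast. No within-arm test, alpha or decision rule is specified, the Aim 2a objective is descriptive and covers both arms, and this is a feasibility pilot. All of that stands, and it confines the point to one hypothesis and one unnamed contrast. It does not repair the hypothesis, which still predicts improvement in one arm without reference to the other.

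The evidence of decline is also narrow, which stands too. The Background gives no course for self-efficacy, depression, anxiety or overall QOL, and nothing after RT.

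A third reply is that a pilot of this size has little power for any contrast. For e = 0.3, the between-arm test of change would be significant with probability 0.15 at r = 0.5 and 0.22 at r = 0.7. That is correct. The reason for the between-arm contrast is that it estimates the right quantity, with an interval showing how imprecisely it is known.

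A reader might go further and infer that an inert intervention would appear to work because caregivers recover by T3. Such recovery would have that effect: an assumed 0.3 to 0.5 SD gives a significant within-arm improvement in 25% to 78% of trials at n = 20 and r = 0.5 to 0.7. But the documents report nothing on recovery, and the intervention is delivered during RT, which makes T2 the more natural reading of post-intervention. This remains a hypothetical risk.

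**Conclusion.** The point holds in a limited form. The Aim 2a hypothesis mixes natural drift with the intervention effect, and it leaves the post-intervention visit undefined. For the burden domains where the team reports decline, the documented risk is a missed benefit: an intervention that just offsets the decline gives zero expected change and a probability of 0.025 of showing improvement, at any visit correlation. The algebra needs no assumed values; the other probabilities depend on assumed SD-unit inputs and show direction only.

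Two stronger readings are not supported. One is that the Aim 2a result would reflect the natural course instead of the intervention. It reflects the sum of both, and under the reported worsening an improvement by T2 could not be put down to that trend. The other is that the trial disregards its control arm. Aim 2b, the Aim 3 hypothesis and the mixed model all use it. No feasibility result and no planned between-arm estimate is affected.

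**What to change.** - Make within-arm change from T1 descriptive, reported for both arms, with no improvement hypothesis attached to the intervention arm alone.
- Define post-intervention as T2, with T3 as follow-up.
- Base the improvement hypothesis on the between-arm difference at T2 (and T3) relative to T1, with a 95% CI, from the planned mixed model. Preferably adjust for the T1 value or constrain the arms to a common T1 mean, since a plain change contrast is less precise than the T2 level contrast when the visit correlation is below 0.5.
- Say that this contrast supplies the effect-size estimate for the larger study.

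The cost is a rewording of the hypothesis and one named contrast in the Analytical Plan. No new data, visits or participants are needed. The adjusted form changes how T1 enters the existing model; the plain change contrast can be read from that model as it stands.

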(1) has a current cancer diagnosis, (2) cannot read/ communicate in English, (3) Caregivers who have an endocrine disorder (e.g., diabetes and thyroid disorders), or is currently taking a steroid-based medication will not be eligible to participate in the saliva portion of the study.

Care-recipients

- **Inclusion Criteria**

(1) has a new or recurrent AJCC stage I-IV squamous cell carcinoma of the upper aerodigestive tract (including lip/oral cavity, nasopharynx, salivary gland, oropharynx, hypopharynx, paranasal sinus, and larynx cancers), (2) has planned external beam radiotherapy (+/- chemotherapy) for 6-7 weeks, (3) ≥ 18 years of age, and (4) has an informal (unpaid) caregiver during RT who is participating in study.

- **Exclusion Criteria**

(1) cannot read/ communicate in English.

- **Sample Size**

The sample size is based on feasibility (Aim 1). Our primary feasibility measures are participation and retention rates. About 110 patients present to our outpatient radiation clinic for treatment per year (9/mo). Based on previous experience, we expect approximately 75% of patients (n = 82) will have a caregiver and at least 75 patient-caregiver dyads will meet eligibility criteria (6/mo). With an estimated participation rate (consistent with PI's experience) of 70%, we expect to recruit 40 patient-caregiver dyads within 8-10 months. If we approach 56 participants to recruit 40, we will be able to estimate the participation rate within +/- 12% using a two-sided 95% confidence interval; thus, we can be 95% confident that the true recruitment rate would be between 59% and 83%, which would support that the study is feasible. With 40 participants we can estimate the retention rate within +/- 12%. If the observed retention rate is 80%, we can be 95% confident that the true rate is between 67% and 92%, which would indicate a feasible study.

Interventions and Interactions

After recruitment and randomization, caregivers in the intervention group will meet with the study interventionist to review the intervention.

Overview of Intervention (see Table 1)

The multi-component intervention (or kit), *Prepare to Care*, includes:

- 1) brief introduction video on a DVD,
- 2) binder including eight workbook modules offered in hard copy, and
- 3) CD with audio instructions to facilitate Progressive Muscle Relaxation (PMR) Training (included in module 8).

Modules

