Aim 1: To assess feasibility (accrual, participation, and retention) and acceptability of a supported self-management intervention for psycho-education and stress management skills building designed for

informal caregivers (Intervention Group, n=20; Waitlist Control Group, n=20) of HNC patients undergoing RT.

Accrual rate will be defined as the number of caregivers who agreed to participate divided by the number of months of recruitment. Participation rate will be defined as the percent of eligible participants who agreed to participate. Retention rate will be defined as the number of participants who completed T3 measures divided by the number who consented to participate. Mean accrual rate, participation rate, and retention rates and their associated 95% confidence intervals (CI) will be estimated.

Acceptability will be summarized quantitatively and qualitatively. Descriptive statistics will summarize participants' overall rating of acceptability; ANOVA and regression models will examine if acceptability varies by demographic, caregiving, or patient characteristics. A codebook for analyzing the qualitative interviews will be developed using a thematic analysis procedure, facilitating coding into discrete categories. Interviews will be coded by at least two raters and discrepancies will be discussed until consensus is reached. Frequency counts will be calculated for themes pertinent to caregivers' likes/dislikes.

Aim 2a: To obtain preliminary data on caregiver intermediate (self-efficacy for (a) coping with cancer and (b) abbreviated progressive muscle relaxation) and outcome variables (burden, psychological distress, quality of life) in intervention caregivers and waitlist control caregivers at the start of radiation (T1), end of radiation (T2), and 6-weeks post-radiation (T3).

Aim 2b: To compare intermediate (self-efficacy for (a) coping with cancer and (b) abbreviated progressive muscle relaxation) and outcome variables (burden, psychological distress, quality of life) between intervention caregivers and waitlist control caregivers at T1, T2, and T3.

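### The 95% interval for retention that supports n=40 appears to be a Wald interval, which under-covers at this size; the lower limit is about 64-66% rather than 67% (minor)

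*Combined protocol and SAP*

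**What the plan says.** The Sample Size section gives the basis directly: "The sample size is based on feasibility (Aim 1). Our primary feasibility measures are participation and retention rates". No power or effect-size calculation accompanies n=40. The statistical argument consists of two intervals, alongside a projection of how quickly dyads will accrue.

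- **Participation.** The planning rate is given as "With an estimated participation rate (consistent with PI's experience) of 70" per cent. The precision statement begins "If we approach 56 participants to recruit 40" and continues "we will be able to estimate the participation rate within +/- 12% using a two-sided 95% confidence interval". The conclusion is "we can be 95% confident that the true recruitment rate would be between 59% and 83" per cent.
- **Retention.** "With 40 participants we can estimate the retention rate within +/- 12" per cent, and then "If the observed retention rate is 80%, we can be 95% confident that the true rate is between 67% and 92" per cent. The plan takes this range as a sign of feasibility.

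The Aim 1 paragraph of the Analytical Plan says "Mean accrual rate, participation rate, and retention rates and their associated 95% confidence intervals (CI) will be estimated". Neither place names an interval method, and neither sets a minimum participation or retention rate.

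**The concern.** A symmetric interval of about 12 points around 80% with 40 people suggests the simple normal-approximation (Wald) formula. That formula is known to fall short of its nominal level when n is small and the proportion is well away from one half. The true sampling uncertainty around 80% is not symmetric: it reaches further down than up. For a feasibility claim the lower limit matters most, so an interval that sits too high flatters the result at that end.

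Two things are at stake. One is the accuracy of the 95% confidence attached to the retention figure that supports the sample size. The other is the analysis: with no method named, the team could report Wald by default, or choose a method after seeing the data, for its two primary feasibility measures.

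**Working it through.** **Inputs (all from Sample Size).** Two-sided 95%, so z = 1.96. Retention 80% of 40 = 32/40. Participation 40/56 = 71.4%. Printed limits: 67-92% and 59-83%.

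**1. Reproduce the plan's figures (Wald).** Half-width = z × √(p(1−p)/n).

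- Retention: 1.96 × √(0.80 × 0.20/40) = 1.96 × 0.0632 = 12.4 points, giving 67.6% to 92.4%.
- Participation: 1.96 × √(0.714 × 0.286/56) = 1.96 × 0.0604 = 11.8 points, giving 59.6% to 83.3%.

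Dropping the decimals gives all four printed limits, and both half-widths round to 12. The only internal slip is one point: 80 − 12 = 68, and 67.6 rounds to 68, but 67 is printed.

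**2. Coverage of the Wald interval for retention.** Take a true rate of 80% and X ~ Binomial(40, 0.80).

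- The lower limit lies above 80% when X ≥ 36. At 36/40 it is 0.90 − 1.96 × √(0.09/40) = 0.807. P(X ≥ 36) = 7.6%, against a nominal 2.5%.
- The upper limit lies below 80% when X ≤ 26. At 26/40 it is 0.65 + 1.96 × √(0.2275/40) = 0.798. P(X ≤ 26) = 1.9%.
- Coverage = 100 − 7.6 − 1.9 = 90.5%.

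Coverage of a binomial interval jumps as the true rate changes, so one value is not enough. The same sum gives:

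| Method, n=40 | True rate 80% | Average over 70-90% |
|---|---|---|
| Wald | 90.5% | 92.4% |
| Wilson | 92.8% | 95.2% |
| Exact (Clopper-Pearson) | 97.3% | 97.0% |

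**3. Retention by other methods, 32/40.**

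Wilson: limits = [p + z²/2n ± z√(p(1−p)/n + z²/4n²)] / (1 + z²/n). With z² = 3.84, the centre is (0.80 + 0.0480)/1.0960 = 0.774 and the half-width is 1.96 × √(0.0040 + 0.0006)/1.0960 = 0.121.

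Exact: lower limit = 2.5% point of Beta(32, 9); upper limit = 97.5% point of Beta(33, 8).

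| Method | Interval | Arms around 80% |
|---|---|---|
| Wald | 67.6-92.4% | −12.4 / +12.4 |
| Wilson | 65.2-89.5% | −14.8 / +9.5 |
| Exact | 64.4-90.9% | −15.6 / +10.9 |
| Agresti-Coull | 65.0-89.8% | −15.0 / +9.8 |
| Jeffreys | 65.8-90.1% | −14.2 / +10.1 |
| Mid-P | 65.5-90.3% | −14.5 / +10.3 |

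Every lower limit from Wilson down is below the printed 67%.

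**4. Participation, 40/56.** Wilson gives 58.5-81.6% and exact 57.8-82.7%, against the printed 59-83%. Wald coverage with n=56 is 95.7% at the 70% planning rate and 93.7% at 71.4%.

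**The case against.** The strongest case against the point is that the plan's figures are reproducible and nothing turns on the difference. Much of that stands.

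- **A reader might infer that the intervals contradict the stated 12 points.** They do not. Both half-widths round to 12, and 59-83 is 71 ± 12. The one-point slip at 67 comes from truncation and makes the printed interval slightly wider, so it is on the cautious side. This is a question of method and not an arithmetic error.
- **A reader might infer that 64% is the one correct lower limit.** It is not. It is the exact limit, and the exact method is conservative (97.3% coverage at 80%). Other accepted methods give 65-66%.
- **The 90.5% is a local low.** Wald coverage is 93.1% at a true rate of 79% and 94.8% at 81%, and Wilson also misses 95% at exactly 80%. This is fair, and it is why the average is the better summary. Over 70-90% Wilson averages 95.2% and Wald 92.4%, so the shortfall is not an artefact of one value.
- **A reader might fault the participation interval for being centred on 71.4% rather than 70%.** The plan supposes 40 recruited out of 56, and an interval is centred on the observed proportion. At exactly 70% with n=56 the half-width is still 12.0 points.
- **The analysis is not committed to Wald.** This is true: the Aim 1 text names no method and could already lead to Wilson or exact. It is also the reason to name one.

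**Conclusion.** The point holds for retention and is minor. With 40 caregivers the interval that fits the printed limits has less than the stated 95% confidence: 90.5% at a true rate of 80%, and about 92.4% on average over 70-90%. At 80% the lower limit is too high three times as often as it should be (7.6% against 2.5%). With an observed 32/40, the lower limit is about 64-66%. This is some 2-3 points below the Wald value of 67.6%, and the downside is about 14-16 points rather than 12. For participation the change is about 1-2 points, and Wald coverage at the planning rate is close to nominal, so a general claim that 95% confidence is not delivered would go too far.

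A reader might also infer that n=40 is inadequate or that the feasibility conclusion fails. The documents do not support that: they define no minimum rate, so no stated criterion is crossed.

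The conclusion assumes that the limits were computed by the Wald formula, which is inferred from the match of all four printed values. It also assumes that caregivers are retained independently with a common probability, and that 40 and 56 are fixed denominators.

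**What to change.** Keep n=40.

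1. In Sample Size, restate retention as 80% (32/40) with either the Wilson interval, 65.2-89.5% (−14.8/+9.5 points), or the exact interval, 64.4-90.9% (−15.6/+10.9 points). Drop the symmetric 12-point statement.
2. Restate participation (40/56, 71.4%) by the same method: Wilson 58.5-81.6% or exact 57.8-82.7%.
3. In the Aim 1 paragraph of the Analytical Plan, name that method for the participation and retention intervals. Either choice is defensible: Wilson is close to 95% on average, and exact never falls below it.

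The cost is a few sentences. Design, sample size and data collection are unchanged. The only downside is that the stated precision becomes slightly less favourable.
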